11.6 Multiple testing

In the primary analysis we will test the 3 hypotheses outlined in section 7.1. As placebo is not used in practice, we do not consider tests involving Arm 3 as one of our multiple comparisons. For the primary analysis the alpha level is adjusted to 0.0167 to account for 3 comparisons. Secondary hypotheses and outcomes will not be adjusted for multiple testing.

12 Analysis of Safety Endpoints

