7.1 Primary Objective

To conduct a multicenter, parallel, four-arm randomized controlled trial that will establish the efficacy of various components of the typical PT regimen for subjects 45-85 with symptomatic meniscal tear. The four arms will include:

- Arm 1: Prescription of an information-based (exercise pamphlet, DVD) home exercise program
- Arm 2: An information-based home exercise program (exercise pamphlet, DVD) with adherence optimization
- Arm 3: Same as Arm 2 plus a clinic-based, therapist-directed sham intervention, with no known physiologic effect
- Arm 4: Same as Arm 2 plus "true PT": clinic-based, therapist-directed exercise and manual therapy

The three primary hypotheses are:

Therapist-directed exercise and manual therapy plus optimized home exercise (Group 4) will lead to greater improvement in KOOS pain at three months than simple prescription of a home exercise program (Group 1).

Therapist-directed exercise and manual therapy plus optimized home exercise (Group 4) will lead to greater improvement in KOOS pain at three months than optimized home exercise and no interaction with a therapist (Group 2).

Optimized home exercises (Group 2) will have a greater effect on KOOS pain at three months than simple prescription of exercises without adherence optimization (Group 1).

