8.3 Blinding

This trial is a single-blind study. The Analysis Core, including the Statistician and Principal Investigator, will be blinded to the subject's treatment assignment to avoid bias. Research coordinators communicating with the TeMPO subjects about outcomes assessment and performing follow-up assessments (i.e., performance tests, strength testing) are blinded to the subject's arm assignment. All other individuals, including the study subject, are not blinded. All subjects will be told during the informed consent procedure that this study has a placebo element. However, we will not specify what the placebo element is. Subjects will also be informed that all groups will receive at least some active intervention. The analysis will be done with group status masked; identification of each arm will not be revealed until the analyses are completed.

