8.5 Sample Size

We power the trial to detect a modest effect of 0.33 SD, reasoning that patients and clinicians will adopt treatments with modest effects if the intensity of treatment and risk of harm is low. As the KOOS Pain scale had a baseline SD of 16 points in MeTeOR, an effect size of 0.33 SD equates to 5.3 points, less than the estimated minimally clinically important difference for the KOOS Pain scale of 8-10 points^{9,13}. We envision that the difference between Arm 1 (least intensive) and Arm 4 (most intensive) will be 10-12 points and that the comparisons of Arms 1 vs. 2 (effect of adherence optimization), 2 vs. 3 (additional provider interaction), and 3 vs. 4 (additional therapist-directed exercise and manual therapy) will represent components of this overall difference. Thus, our plan to power for a difference of 5.3 points in pairwise comparisons should provide adequate power for all contrasts. We assume 80% power and Type I error of 0.0167 to reflect three comparisons of strategies that would be used in practice (Arms 4 vs. 1; Arms 4 vs. 2; Arms 2 vs. 1). Given these considerations and balanced allocation across arms, each Arm would need 194 subjects. Allowing for 10% dropout at one year we will require 194 x 1.1 = 214 subjects per Arm, 856 in total.

9 Analytic Considerations

9.1 Hypotheses

This study will address the following hypotheses, summarized in Table 2:

| Table 2. Study Hypotheses | | | | | | | | | | | |
|---------------------------|-----------------------|--|-----------------------|------------------------------------|--|--|--|--|--|--|--|
| Arm | Arm 1 (home exercise) | Arm 2 (home exercise w/adherence optimization) | Arm 3 (placebo PT) | Arm 4 (therapist- delivered PT) | | | | | | | |
| Arm 1 | | | | | | | | | | | |
| Arm 2 | H3 | | | | | | | | | | |
| Arm 3 | | H4 | | | | | | | | | |
| Arm 4 | H1 | H2 | H5 | | | | | | | | |

Primary Hypotheses:

Hypothesis 1: Arm 4 (protocolized home program, adherence optimization, in-clinic physical therapist-delivered exercise and manual therapy) is more efficacious than Arm 1 (protocolized home program alone). This analysis contrasts the putatively most potent intervention against the least potent.

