11.1 Primary Analysis

In the primary analysis we will test the 3 hypotheses outlined in section 7.1. As placebo is not used in practice, we do not consider tests involving Arm 3 as one of our multiple comparisons. For the primary analysis the alpha level is adjusted to 0.0167 to account for 3 comparisons. We will adjust for randomization arm, the randomization stratification factors of study site and baseline KL grade (0-2 vs. 3) as well as baseline KOOS pain and enrollment date (prior to or after March 15, 2020).

We will use linear regression as our main analytic approach, as our primary outcome of change in KOOS pain is continuous. The primary analysis will be complete case. Data will be summarized by treatment group with the number, mean, and standard deviation. 98.3% Cis will be used to summarize the three between-group comparisons of interest.

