11.5 Statistical analyses to handle missing data

We anticipate ~5% dropout at 3 months and ~10% at 12 months based on dropout rates from the Meniscal Tear in Osteoarthritis Research (MeTeOR) RCT⁹. We will address dropout and other forms of missing data first by reporting the number of subjects dropping out in each arm and the reasons for dropout. We will determine whether the frequency of these dropouts differs across study arms. We will examine the distribution of baseline covariates and baseline KOOS pain in subjects dropping out compared to those completing the study. Our primary assumptions

are that data will be missing at random (MAR), and that dropout will not depend on unobserved outcomes.

We will perform sensitivity analysis for missing data for our primary outcome of KOOS pain and our secondary outcomes of KOOS ADL, EQ-5D, strength measures, objective function measures, and treatment failure for our three primary hypotheses. We will use linear mixed effects models to analyze the continuous outcomes of KOOS pain, KOOS ADL, and EQ-5D. Models will be adjusted for timepoint, randomization arm, the randomization stratification factors of study site and baseline KL grade (0-2 vs. 3) as well as the baseline value of the outcome and enrollment date (prior to or after March 15, 2020). A timepoint by treatment arm interaction term will test whether change from baseline to 3 months differs between treatment arms. Linear mixed-effects models can handle imbalanced data and are appropriate for data that are missing at random.

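### Testing the three primary hypotheses at a fixed 0.0167 is valid but conservative; Holm's step-down rule keeps 5% familywise error and adds 0 to 17 points of power per hypothesis

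*SAP*

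**What the plan says.** SAP 7.1 names three primary hypotheses on three-month change in KOOS Pain: H1 (Arm 4 vs 1), H2 (Arm 4 vs 2) and H3 (Arm 2 vs 1). All three are expected to be true; H3, for example, reads "Optimized home exercises (Group 2) will have a greater effect on KOOS pain at three months than simple prescription of exercises". Contrasts with Arm 3 are secondary and unadjusted.

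Sections 11.1 and 11.6 set one level for each primary test: "For the primary analysis the alpha level is adjusted to 0.0167 to account for 3 comparisons". Section 11.1 adds that "98.3% Cis will be used to summarize the three between-group comparisons of interest", and the code in 13.3 and shell Table 2 use the same level. No ordering or step-down rule is given.

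The sample size in 8.5 rests on the same level: "We assume 80% power and Type I error of 0.0167 to reflect three comparisons of strategies that would be used in practice". On effect sizes it says "We envision that the difference between Arm 1 (least intensive) and Arm 4 (most intensive) will be 10-12 points", and that the stepwise contrasts between neighbouring arms "will represent components of this overall difference".

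**The concern.** A fixed 0.0167 for each test leaves error rate unused once one hypothesis has been rejected. The SAP expects Arm 4 to beat Arm 1 by 10-12 points, so H1 is almost certain to be rejected (power above 99.9%). At that point at most one of the other two null hypotheses can be true, because Arms 1, 2 and 4 are no longer all equal. Continuing to test H2 and H3 at 0.0167 then holds the familywise error to about 1.7%, not 5%.

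H2 and H3 bear the cost. H3 is the more exposed, because the adherence programme is expected to supply only part of the 10-12 points. A missed H3 would leave one of the trial's three primary questions unanswered for lack of power that needs no further participants.

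**Working it through.** **Inputs.** Alpha 0.0167, 80% power, 0.33 SD, SD 16, 5.3 points, 194 per arm, 10-12 points for Arm 4 vs 1 (all 8.5); three pairwise tests among Arms 1, 2 and 4 (11.6); about 5% dropout at three months (11.5), so 214 × 0.95 ≈ 203 evaluable per arm.

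**The SAP's own figure.** n = 2(z₁₋α/₂ + z₁₋β)²/d² = 2(2.393 + 0.842)²/0.33² = 192.2 per arm; the t-based version gives 193.6, rounded up to 194. This reproduces the SAP. A one-sided test would need only about 162, so the tests are two-sided although the SAP does not say so.

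**Power for a single contrast.** SE = 16√(2/194) = 1.62. Power ≈ Φ(δ/SE − z).

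| True difference | at 0.0167 (z = 2.393) | at 0.05 (z = 1.960) |
|---|---|---|
| 5.3 | 80.8% | 90.4% |
| 8 | 99.4% | 99.8% |
| 10 | above 99.9% | above 99.9% |

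**Ceiling on the gain.** At best a hypothesis moves from 0.0167 to 0.05. The difference in power is largest when δ/SE = (2.393 + 1.960)/2 = 2.177, where it is Φ(0.217) − Φ(−0.217) = 0.17. In KOOS points that is 2.177 × 1.62 = 3.5.

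**Rules compared.**
- Fixed: every p-value against 0.0167.
- Holm: ordered p-values against 0.0167, 0.025 and 0.05, stopping at the first that fails.
- Shaffer: smallest p-value against 0.0167; if it passes, the other two against 0.05. This is valid because, among three arms, once one pair differs at most one other pair can be equal.

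Results come from 1,000,000 simulated sets of three arm means per scenario, with two-sided z tests, 194 per arm and SD 16. The SAP does not split its 10-12 points, so the H3 effect is an assumption shown over a range.

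| Means, Arms 1/2/4 | Quantity | Fixed | Holm | Shaffer |
|---|---|---|---|---|
| 0/5.3/10.6 | H2, H3 (each) | 81% | 90% | 90% |
| 0/5.3/10.6 | all three | 62% | 81% | 81% |
| 0/2/10 | H3 | 12% | 23% | 23% |
| 0/3.33/10 | H3 | 37% | 53% | 54% |
| 0/4/12 | H3 | 53% | 69% | 69% |
| 0/5/10 | H3 | 75% | 86% | 87% |
| 0/6/12 | H3 | 90% | 96% | 96% |
| 0/0/5.3 | H1, H2 (each) | 81% | 84% | 87% |
| 0/0/5.3 | at least one | 91.8% | 91.8% | 91.8% |

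**Familywise error.** With all means equal it is 4.4% under every rule. At 0/0/5.3 it is 1.7% (fixed), 3.7% (Holm) and 5.0% (Shaffer). At 0/0/12 it is 1.7%, 5.0% and 5.0%. No simulated trial had a fixed-rule rejection that either step-down rule missed.

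**Sensitivity.**
- With 203 per arm: at 0/5.3/10.6, H2 goes from 83% to 91% (Holm). With an equal three-way split of 10-12 points, H3 goes from 38-55% to 55-71%.
- The primary model adjusts for baseline KOOS Pain. If the baseline/three-month correlation ρ is 0.3, 0.5 or 0.6 (assumed, with equal SDs), the residual SD is 16√(1 − ρ²). With 203 per arm at 0/5.3/10.6, H2 goes from 87% to 94%, 93% to 97% and 96% to 99%; Holm and Shaffer agree to rounding.

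**Agreement with the intervals.** At 0/5.3/10.6, about 19% of trials would reject at least one hypothesis whose 98.3% interval includes zero (either step-down rule). At 0/0/5.3 the figure is about 7% with Holm and 15% with Shaffer.

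**The case against.** The SAP's rule is valid and consistent across 8.5, 11.1, 11.6, 13.3 and shell Table 2, and it meets its stated target of 80% power per contrast. The SAP never asks for all three hypotheses to be rejected, and the chance of at least one rejection is the same under every rule. A fixed level also makes each interval agree with its test, which is a fair reason to choose it. The largest gain falls at 3.5 points, below both the 5.3 points powered for and the 8-10 points the SAP cites as clinically important. If Arms 1 and 2 are truly equal, the chance of a false H3 claim rises from 1.7% to between 3.7% and 5.0%. Loosening a rejection rule in a plan signed in March 2024 could also look opportunistic.

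All of this is accurate, and it makes the point an improvement, not a correction. It does not remove the case for it. The higher H3 error stays within the 5% familywise rate the SAP itself chose. The SAP does power for 5.3 points, where the gain is nearly 10 points before baseline adjustment. The mismatch with the intervals is a real cost, met by showing both intervals. The concern about timing is met by limiting the change to the period before any outcome analysis.

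**Conclusion.** The fixed 0.0167 is valid but gives away power. Holm never rejects less and keeps familywise error at most 5%. It adds about 9 to 10 points each for H2 and H3 at the 5.3-point difference the SAP powers for, and up to 17 points where a component is 3 to 4 points. It adds essentially nothing for H1 if Arm 4 vs 1 is 10-12 points, and nothing of note for any contrast of 8 points or more.

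These sizes assume SD 16, 194 per arm and the stated splits of the 10-12 points. At 5.3 points with 203 per arm, an assumed baseline correlation of 0.3 to 0.6 reduces the gain to between about 7 and 2 points. The change is worth making if no outcome analysis has been run; the SAP does not show whether one has.

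**What to change.** State in 11.1 and 11.6: H1-H3 are tested two-sided by Holm's step-down procedure, with ordered p-values against 0.0167, 0.025 and 0.05, stopping at the first that fails; familywise error is at most 5%; the rule applies to the primary analysis only.

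Shaffer's rule is an acceptable alternative. It adds almost nothing to Holm if Arm 4 vs 1 is 10-12 points, and about 3 points for H1 and H2 at 0/0/5.3. The order must come from the p-values. A fixed order H1, H2, H3 can lose power: at 0/6.67/10, H3 falls from 96% to 52%.

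Keep the 98.3% intervals as simultaneous intervals. Add 95% intervals through a second LSMEANS line with ALPHA=0.05 in 13.3 and one extra interval per contrast in shell Table 2. Add a note that a hypothesis rejected at a later step may have a 98.3% interval that includes zero.

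The change must be fixed before any outcome analysis is run, masked or not. Before unmasking is too late, because under 8.3 "identification of each arm will not be revealed until the analyses are completed". If any outcome analysis has been run, keep 0.0167.

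The cost is this wording, one code line and one table entry per contrast. The sample size and model do not change, and 8.5 stands as a conservative calculation. The price is that decisions no longer match the 98.3% intervals one to one.

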12.1 Adverse events

The number and percentages of adverse events (Aes) will be summarized in total and for each treatment arm. The severity and relatedness of each adverse event to the study will be broken down by intervention. Adverse events include:

- any risk specific to physical therapy or to exercise including an episode or exacerbation of musculoskeletal pain (knee, hip, back, neck). Musculoskeletal discomfort is common after exercise and to be expected. Thus, we have defined a musculoskeletal adverse event as requiring a level of severity that precluded walking for one day or more or that that required the subject to rely upon an assistive device such as a cane or crutch for at least one day to ambulate.
- Any risk related to topical treatments (ultrasound, gel) such rash or pruritis (itching).

12.2 Serious adverse events

As with AEs, the number and percentages of serious adverse events (SAEs) will be summarized in total and for each treatment arm. The relatedness and type of each SAE will be broken down by treatment arm. Serious adverse events include:

- Death from any cause
- Overnight hospital admission as a result of medical problems such as myocardial infarction, stoke, pulmonary embolus, congestive heart failure decompensation, pneumonia, serious infection
- Overnight hospital admission as a result of surgical problems such as emergent surgery (e.g. cholecystectomy for biliary sepsis, acute appendicitis or diverticulitis)
- Arthroscopic partial meniscectomy (APM)
- Total knee replacement (TKR)

12.3 Analysis for AEs and SAEs

We anticipate few AEs and negligible SAEs. We will present these endpoints descriptively. We will aggregate AEs and compare the number of AEs across the four arms using a Kruskall-Wallis Test or Fisher's exact test if the numbers are small.

13 Derived Variable Definitions, Coding, and QC Plan

13.1 Derived Variable Definitions and Coding

KOOS Pain^{20,21}: The KOOS is a knee-specific self-administrated instrument, to assess the patients' opinion about their knee and associated problems. The KOOS evaluates five separately scored outcomes: Pain, other Symptoms, Function in daily living (ADL), Function in Sport and Recreation (Sport/Rec), and knee-related Quality of Life (QOL).

KOOS Pain has 9 items and asks the amount of knee pain experienced in the last week. A Likert scale is used, and all items have five possible answer options scored from 0 (No problems) to 4 (Extreme problems) and each of the five scores is calculated as the sum of the items included. We will normalize raw KOOS Pain score to 100 (with 100 being the worst), by applying the mean of the observed items within the KOOS Pain, dividing by 4, and multiplying by 100. Formular is provided below:

KOOSPain= Mean (KoosP_1 -- KoosP_9)/4 * 100

As long as at least 50% of the subscale items are answered for each subscale, a mean score can be calculated. If more than 50% of the subscale items are omitted, the response is considered invalid, and no subscale score should be calculated. For KOOS Pain, a valid score requires at least 5 non-missing items.

KOOS ADL^{20,21}: KOOS Function in daily living (ADL) has 10 items and ask about physical function. A Likert scale is used, and all items have five possible answer options scored from 0 (No problems) to 4 (Extreme problems) and each of the five scores is calculated as the sum of the items included. We will normalize raw KOOS ADL score to 100 (with 100 being the worst), by applying the mean of the observed items within the KOOS ADL, dividing by 4, and multiplying by 100. Formular is provided below:

KOOSADL= Mean (KoosDailyLV_1 -- KoosDailyLV_10)/4 * 100

For KOOS ADL, a valid score requires at least 6 non-missing items.

EQ-5D^22: EQ-5D measures health using five levels of severity in five dimensions, including mobility, self-care, usual activities, pain/discomfort, anxiety/depression. Each dimension now has 5 levels: no problems, slight problems, moderate problems, severe problems, and extreme problems. The respondent is asked to indicate his/her health state by choosing the most appropriate statement in each of the 5 dimensions. This decision results in a 1-digit number expressing the level selected for that dimension. The digits for 5 dimensions can be combined in a 5-digit number describing the respondent's health state. The numbers 1-5 have no arithmetic properties. The coding for EQ-5D-5L is publicly available on EuroQoL website. The final EQ5D score ranges from 0 to 1 with 1 being the best health. A valid EQ-5D-5L score requires non-missing for all five dimensions.

Treatment Durability: Treatment durability assessed whether the treatment effect lasts beyond 3 months. This is defined only for those participants achieving ≥ 8 point improvement in KOOS pain from baseline to 3 months. Treatment durability is not defined for participants failing to achieve at least an 8 point improvement in KOOS pain or who undergo APM or injection prior to the 3 month visit. Treatment durability will be defined as maintaining at least an 8-point improvement from baseline at the 12-month follow-up, without undergoing APM or injection. Participants failing to maintain an 8-point improvement from baseline or undergoing APM or injection between 3 months and 12 months will be coded as not having treatment durability.

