9.2 Primary outcome

The primary outcome in this trial is change in the KOOS Pain score from baseline to 3 months.

9.3 Secondary outcomes:

- Baseline to 3 month change in KOOS ADL
- Baseline to 3 month change in EQ-5D
- Treatment failure at 3 months
 - Defined as failing to achieve an 8-point improvement in KOOS pain from baseline and/or receiving injection or undergoing knee surgery prior to 3 months
- Baseline to 3 month change in 40 meter face-paced walk
- Baseline to 3 month change in number of repetitions in sit-to-stand test
- Baseline to 3 month change in single leg balance
- Baseline to 3 month change in muscle strength
 - o Quadriceps
 - o Hamstrings
 - o Gluteus medius
- Durability of pain relief
 - o Treatment Durability: Defined only for those participants achieving ≥ 8 point improvement in KOOS pain from baseline to 3 months, and who did not have an injection or knee surgery during this interval. Treatment durability will be defined as maintaining at least an 8-point improvement at the 12-month follow-up. Participants who receive injection or had knee surgery between 3 and 12-months will be classified as failing to achieve treatment durability.
- Longitudinal Outcomes:
 - KOOS pain at 3, 6, and 12 months
 - KOOS ADL at 3, 6, and 12 months

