10.1 Participant Disposition

Participant disposition will be summarized in a CONSORT diagram.¹⁴ This will include the number of patients screened for eligibility, the number of patients eligible, the number of patients interested, the number of patients randomized, and the number of patients randomized to each treatment group. The reasons for ineligibility will also be summarized as part of the CONSORT diagram.

Visit completion status and the reason for early discontinuation of the study will be summarized by site and treatment arm with descriptive statistics. These include the number and percentage of each reason for discontinuation. We will also summarize the number and percent of participants undergoing APM by timepoint and undergoing injection by timepoint.

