11.2.2.2 Treatment Durability

We will assess treatment durability descriptively as the number and percent of participants in each arm meeting the criteria specified in 9.3. We will report alongside these results the number and percent of participants eligible for the durability analyses (meaning that they achieved improvement of ≥8 points on KOOS Pain between baseline and 3 months, in the absence of surgical intervention or injection).

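### The treatment durability coding rule in SAP 13.1 disqualifies only for APM or injection, while 9.3, the definition the analysis applies, disqualifies for injection or any knee surgery

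*SAP*

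**What the plan says.** Durability is defined or restated in three places in the SAP.

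- **Section 9.3 (secondary outcomes).** Durability is defined for participants who gained at least 8 points on KOOS Pain by 3 months and "who did not have an injection or knee surgery during this interval". For the later period: "Participants who receive injection or had knee surgery between 3 and 12-months will be classified as failing to achieve treatment durability".
- **Section 11.2.2.2 (analysis).** The result reported is "the number and percent of participants in each arm meeting the criteria specified in 9.3". The eligible set is restated as 3-month responders "in the absence of surgical intervention or injection".
- **Section 13.1 (derived variables and coding).** Durability is undefined for those who do not reach 8 points "or who undergo APM or injection prior to the 3 month visit". Success is a maintained 8-point gain at 12 months "without undergoing APM or injection". Failure includes those "undergoing APM or injection between 3 months and 12 months will be coded as not having treatment durability".

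Section 10.1 plans a count of "participants undergoing APM by timepoint and undergoing injection by timepoint". Sections 5 and 12.2 and shell Table 3 list TKR as an item separate from APM.

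**The concern.** Sections 9.3 and 11.2.2.2 disqualify for knee surgery in general. Section 13.1 disqualifies for one operation, and does so in its eligibility, success and failure conditions alike, so the narrower term is not an isolated slip. Nothing in the SAP says that knee surgery means APM only, or that APM stands for every knee operation. The related endpoint in 9.3, treatment failure at 3 months, also uses injection or knee surgery.

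Section 13.1 is where a programmer will look for the derivation. If it is programmed as written, improvement that follows a knee replacement counts as lasting benefit of the randomized arm, which is contrary to the definition that the analysis section cites. The independent reproduction in 13.2 would not be expected to catch this. It covers the primary analyses and Table 2, which has no durability row; durability is reported in an appendix table.

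**Working it through.** The SAP gives no figure to reproduce, so the check is a comparison of the rules followed by a per-case size.

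**The rules applied to the same participant**

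| 3-month responder, no APM, no injection | 9.3 and 11.2.2.2 | 13.1 |
|---|---|---|
| TKR or other non-APM knee operation in months 3-12, at least 8 points better at 12 months | Not durable | Durable |
| Non-APM knee operation before 3 months | Outside the durability set | Inside the durability set |

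The first row changes the numerator. The second changes the denominator, and may also change the numerator.

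**Inputs**

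- 214 randomized per arm (8.5).
- About 5% dropout at 3 months (11.5).
- Assumed: 50-65% of those remaining are eligible for durability. The SAP gives no responder rate.
- Assumed: 50-80% of eligible participants are durable. The SAP gives no rate.
- Assumed: everyone eligible at 3 months stays in the denominator.

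**Eligible per arm, D**

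- 214 × 0.95 × 0.50 = 101.65, about 102
- 214 × 0.95 × 0.65 = 132.1, about 132

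**One late operation (months 3-12), coded durable instead of not durable: change = 1/D**

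- 1/132 = 0.76 percentage point
- 1/102 = 0.98 percentage point

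**One early operation (before 3 months): D becomes D + 1, with durable share p**

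- If coded durable, change = (1 − p)/(D + 1). Smallest: 0.20/133 = +0.15 point. Largest: 0.50/103 = +0.49 point.
- If coded not durable, change = −p/(D + 1). Smallest: −0.50/133 = −0.38 point. Largest: −0.80/103 = −0.78 point.

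**Lower bound.** With no affected participants, the change is 0.

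**Sensitivity to the denominator.** If only participants with 12-month data are counted, using the SAP's figure of about 10% dropout at 12 months, D is 214 × 0.90 × 0.50 = 96 to 214 × 0.90 × 0.65 = 125. One late case is then 1/125 = 0.80 to 1/96 = 1.04 points.

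**The case against.** The best defence is that the SAP largely settles the matter itself. Section 11.2.2.2 names 9.3 as the source of the criteria, so a statistician working from the analysis section would apply the broader rule, and 13.1 is merely the outlier. That helps in choosing the list, but it does not remove the conflict: 13.1 is the coding section, and someone who follows it is following the plan.

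The second point is that very few participants can be affected. A late case must respond at 3 months, have a non-APM knee operation without APM or injection, and still be 8 points better at 12 months. KL grade runs only to 3 in the stratification and in shell Table 1, 12.3 anticipates negligible SAEs (a category that includes TKR), and TKRs are counted by arm in shell Table 3 in any case. This stands, and it is why the point is minor.

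Third, the percentages rest on assumed responder and durable shares, and the choice of denominator moves them. This also stands. What the documents support is roughly one percentage point or less per affected participant, with the number of such participants unknown and possibly zero.

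Fourth, 10.1 uses the narrower wording too. But 10.1 is a disposition summary and defines no endpoint, so it does not show which list was meant for durability.

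Finally, knee surgery is itself undefined: 9.3 does not say which operations count, or whether only the index knee matters. Aligning 13.1 with 9.3 makes the plan consistent but leaves that open.

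**Conclusion.** The concern holds. One endpoint has two lists of disqualifying events, and the coding section departs from the definition that the analysis section applies. Both the numerator and the denominator of the durability percentage can differ between them.

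The severity is minor. Durability is a secondary outcome, presented descriptively in an appendix table with no hypothesis test, and the primary analysis is untouched. The shift may be nil. Otherwise it is below or about one percentage point in an arm for each affected participant, under the assumptions listed with the calculation. Confidence in the contradiction itself is high, because it rests on the text and not on those assumptions.

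**What to change.** Replace APM or injection with injection or knee surgery in all three conditions of 13.1, since 11.2.2.2 names 9.3 as the source of the criteria. Apply the list by event date: before 3 months for eligibility, and between 3 and 12 months for success or failure. In the same edit, state which operations count as knee surgery and whether only the index knee is meant. Check the 10.1 summary so that the events tabulated there are the ones used in the derivation.

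The cost is a few words in 13.1 and a check of 10.1. APM and TKR are listed SAEs in 12.2, and the 8.4 schedule includes an Injection Form, so those events are already captured. The SAP does not say by name how other knee operations are recorded, and that should be confirmed before the derivation is programmed.
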